5 EFFICACY AND SAFETY

5.1 Schedule of Study Assessments

Outcomes will be assessed according the schedule below.

Assessment / Time Point	Birth	3 hours (3 -5 hours)	6 hours	9 hours (6 - 12 hours)	24 hours (20 – 28 hours)	Before 14 days	36 weeks
Consent [#]	х						
ECHOCARDIOGI	RAPHY A	ND RELATED	MEASURE	S			
Bloods/Haemoglobin	х		х				
ECHO		х		х	х		
Cardio-respiratory variables		x		х	х		
Total Fluids			х		х		
Study Specific Fluids		х	х	x	х		
CLINICAL OUTCOM	IES						
Head Ultrasound		х				х	
Nitric Oxide and Hypotension		х		х	х		
Symptomatic Patent Ductus Arteriosus							х

before birth

5.2 Assessments:

5.2.1 Consent

Consent forms must be signed prior to birth and prior to any assessments for this study being conducted.

5.2.2 Blood Collection

Haemoglobin and haematocrit values should be collected at:

- · Baseline from cord bloods (where this is not possible, haemoglobin measures should be collected at admission)
- At 6 hours

5.2.3 Echocardiographic Assessment

All assessments will be de-identified by using a study code and echo number. Echocardiographic assessments will be recorded and stored in a standardized format with a copy stored centrally. The following parameters will be recorded at each echo:

Measures of Systemic Blood Flow:

- · SVC flow (ml/kg/min) will be the median of five measures at each timepoint
- · RVO (ml/kg/min) will be the median of five measures at each timepoint

Effect on the ductus arteriosus:

- Ductal diameter
- Ductal shunt direction %right to left

Page 44 of 81

5.2.4 Cardio-respiratory Variables

The following measures will be recorded at time of the ECHO assessments:

Cardiovascular variables

- 1. Blood pressure:
 - Invasive BP measurement where available will be recorded.
 - Where invasive BP is not available, a validated non-invasive oscillometric device will record BP (mean, systolic, diastolic).
- 2. Heart rate (prior to ECHO measures from monitor)

Respiratory variables

- 1. Respiratory support:
- 2. Mean airway pressure
- $3. \ FiO_2$
- 4. Infant respiratory rate
- 5. Arterial blood gases (ABG) pH, PaCO₂ PaO₂, Bicarbonate, base deficit, lactate. Blood gases may be collected by any means available

5.2.5 Total IV fluids in the first 6 hours and in the first 24 hours

Total IV fluids could be any of the following:

- Maintenance Fluids (ml)
- Normal saline (ml) used for volume expansion
- Fresh Frozen Plasma (ml)
- Albumin (ml)
- Packed Cells (ml)
- Platelets (ml)
- Other volume (ml)
- Intravenous Infusions (ml)
- Intra-arterial infusions (ml)
- IV Medications (ml)

5.2.6 Study-Specific Fluids

Volume expansion and Inotropes (type and volume)

5.2.7 Clinical Outcomes:

- Head ultrasound to assess brain injury (at 3 5 hours)
- Head ultrasound before 14 days (intraventricular haemorrhage) main APTS data
- Incidence of persistent hypotension (>15 minutes) receiving treatment with volume expansion or inotropes or corticosteroids at each ECHO time point.
- Patent ductus arteriosus:
 - Large PDA on first echo
 - DETECT trial drug or indomethacin or ibuprofen in 1st 3 days
 - Treatment for symptomatic PDA (after 3 days age)
 - Indomethacin or ibuprofen
 - PDA ligation
- Nitric oxide

5.2.8 Inter-observer reliability:

All echocardiographs will be recorded and collected centrally. Echocardiography sets for the first 10 babies from each centre will be evaluated by a blinded independent reviewer for accuracy and standardization. After assessment of the first 10 babies, a decision whether to continue with central measurements will be made. In the event that inter-observer reliability is adequate (Intra-class correlation coefficient of absolute agreement >0.70), the echocardiographic measurements will be made at site.

Page 45 of 81

5.2.9 Blinding of assessments

Echocardiographic assessments will be recorded and labelled by study number. Details of treatment allocation will be recorded separately as part of the main APTS trial. Echocardiographic measurements will be made at each study centre by the study fellow in batches blind to infant identity and treatment except for APTS study number and echo timing.

At the time of echocardiography details of ductal diameter, SVC flow and RVO will be given to the clinical team upon the clinical team's request due to clinical concern. However, if infants are detected as having a significant clinically unsuspected cardiovascular problem (SVC flow <41 ml/kg/min or RVO <100 ml/kg/min) this will be communicated by the echocardiography fellow to the clinical team.

5.3 Assessment of Safety

As per APTS protocol. It is not anticipated that clinical echocardiography or blood collection (0.2-0.4ml which may be incorporated into routine clinical measurement) will have an effect on safety requiring additional monitoring beyond that of infants in the main APTS study.

6 STATISTICS

6.1 Sample Size

242 babies yield 90 % power, assuming 2-sided significance (5%) and 20% noncompliance, to detect a relative increase of 27%, from a predicted 55 ml/kg/min in the early cord clamping infants to 70 ml/kg/min in the delayed cord clamping infants ². The sample size is calculated using log-transformed data, with a SD on the log scale of 0.21. All analyses will be performed using intention-to-treat principles.

6.2 Statistical Analysis

The primary analysis will compare the mean SVC flow between the treatment arms using an independent sample t-test on log transformed data. Linear regression may be used as a secondary analysis in order to adjust for any important prognostic factors.

Effect sizes and 95% confidence intervals will be presented for primary and secondary outcomes. For continuous variables, ratios (retransformed mean differences) and 95% confidence intervals for log-transformed variables, differences in means (and standard deviation) or medians (interquartile range) and for dichotomous and categorical factors, relative risks, odds ratios and risk differences will be presented.

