8 STATISTICS

8.1 Sample Size

Controls (early clamping) are expected to have a 30% rate of the primary combined outcome of mortality (10%) and major morbidity (20%) at 36 weeks post menstrual age. A sample size of 1600 would have 90% power to detect a reduction in absolute risk of 8% (27% relative risk reduction) in the primary outcome, allowing for 10% non-compliance at 2p = 0.05. If the non-compliance rate was 20%, this sample size would have more than 80% power to detect a reduction in absolute risk of 8%. About 534 babies are expected to be less than 27 weeks gestation.

The planned sample size of 1600 has 80% power at 2p=0.05 to detect an absolute risk reduction in mortality at 36 weeks post menstrual age of 4.2% from 10% to 5.8% and an absolute risk reduction of 8% (25% - 17%) in the outcome of mortality or severe disability to 24 months corrected gestation, assuming 10% non compliance. It gives 80% power to detect a reduction in absolute risk of major morbidity of 5.9% from 20% to 14.1%, assuming 10% non compliance. The expected sample of 534 babies < 27 weeks gestation gives 80% power to detect an absolute risk reduction of 13.4% from 60% to 46.6% in mortality and major morbidity, assuming 10% non compliance. The expected sample of 1066 babies of 27 ° weeks gestation or more gives 80% power to detect an absolute risk reduction absolute risk reduction of 6.1% from 15% to 8.9% in mortality and major morbidity, assuming 10% non compliance.

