3.3 Randomisation

Timing of randomisation

While consent can be attained at any time, randomisation should only take place when delivery is considered inevitable, for example when labour is considered irreversible or when the operating theatre is booked for Caesarean Section and the baby's estimated gestation is less than 30 weeks gestation. Randomisation should be performed allowing sufficient time to use the Interactive Voice Response System i.e. at least ten minutes before the expected birth, or longer than this for multiple births.

Method of randomisation

Randomisation can be done by any member of the obstetric, midwifery, or neonatal team using a phone to call a computerised interactive voice response system.

Randomisation will be performed by using an interactive voice response system built by an independent statistician at the NHMRC Clinical Trials Centre, University of Sydney. All data will be stored securely by the statistical group at the centre.

Randomisation will be by the method of minimisation with two strata: Institution and Gestational age (<27 weeks; >=27 weeks). Multiple births will be randomised separately.

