Low SVC flow is common in very preterm infants, occurring in over 30% of infants born <30 weeks gestation and >60% of infants <27 weeks gestation.^{17, 20} Low SVC flow is highly predictive of neonatal outcomes. Infants who developed low SBF were at substantially higher risk of mortality, IVH and NEC.^{17, 20, 22} At 3 years of age the infants with low SBF had significantly lower

Page 40 of 81

developmental scores (average 16 DQ points lower) and were at high risk of disability and motor impairments.^{21, 23} Of importance, measures of SBF were better than blood pressure at predicting IVH,¹⁷ mortality and subsequent motor impairments.²⁴ Low SVC flow was also predictive of hyperkalaemia and pulmonary haemorrhage.^{25, 26} Hyperkalaemia has been associated with reduced Na⁺K⁺ATPase activity^{27, 28} (presumably due to tissue ischaemia with cellular energy failure) and impaired renal function. Pulmonary haemorrhage almost always occurs in the reperfusion phase in infants with preceding low SVC flow and large diameter PDA.²⁵

The importance of low systemic and organ blood flows have been confirmed by other groups. Several studies have now demonstrated low systemic and cerebral blood flows are an important risk factor for cerebral injury in preterm infants.²⁹⁻³¹

Risk factors for low systemic blood flow

Risk factors for low SVC (≤40 ml/kg/min) have been consistent between two cohorts of infants studied by our group, and provide a basis for future prevention and treatment trials.^{17, 20} In multivariate analysis, low SVC flow is predicted by lower gestation, an early large diameter DA and almost always occurs in ventilated infants with higher mean airway pressures. Infants with low SVC flow have higher calculated upper body systemic vascular resistance (UBSVR) and worse myocardial contractility as indicated by the relationship between mean velocity of circumferential fractional shortening (mVcfs) and left ventricular (LV) stress.³²

To date, low SBF has not been related to hypovolaemia in preterm infants. Two early studies using albumin labeling techniques^{9, 10} reported that clinical measures such as systemic hypotension were poorly correlated to blood volume in premature infants, suggesting that hypovolaemia is not a substantial factor underlying the cardiovascular maladaptation in the newborn infant.

Cardiovascular support of preterm infants

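### Echo sub-study: the primary t-test ignores gestational age, a minimisation factor that the sub-study itself calls prognostic, so the interval is wider than it need be

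*Supplement*

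**What the plan says.** The sub-study has its own primary outcome, the lowest SVC flow of three measurements in the first day (sub-study 4.4), and its own analysis section. Section 6.2 reads: "The primary analysis will compare the mean SVC flow between the treatment arms using an independent sample t-test on log transformed data". Adjustment is optional and no covariate is named: "Linear regression may be used as a secondary analysis in order to adjust for any important prognostic factors".

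Sub-study infants are those randomised in the main trial at participating centres (sub-study 4.3). Protocol V4.0, section 3.3, sets the allocation: "Randomisation will be by the method of minimisation with two strata: Institution and Gestational age", with the cut at 27 weeks.

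The sub-study background (section 2) treats gestation as prognostic. On risk factors it says: "In multivariate analysis, low SVC flow is predicted by lower gestation". On frequency it describes low SVC flow as "occurring in over 30% of infants born <30 weeks gestation and >60% of infants <27 weeks gestation".

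The sample size (sub-study 6.1) makes no allowance for covariates: "242 babies yield 90 % power, assuming 2-sided significance (5%) and 20% noncompliance", for 55 against 70 ml/kg/min with a log-scale SD of 0.21.

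**The concern.** Balancing the arms on a prognostic factor removes that factor's contribution from the variability of the treatment contrast. A two-sample t-test still counts it in the residual variance. Where the balance holds, the test's standard error is too large and its true size falls below 5%. Where the balance is lost, the test has its nominal size, but the chance imbalance in gestation stays in the estimate. In both cases the interval is wider than one from a model that includes gestation.

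The sub-study asks whether placental transfusion raises or lowers systemic flow. A needlessly wide interval makes a real difference in either direction more likely to be called inconclusive. The optional regression does not cure this. It is not a commitment, and because it names no covariates, the choice could be made after the data are seen.

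**Working it through.** **1. The plan's own figure.** For two means, n per arm = 2(1.96 + 1.2816)² × SD² / δ². If 20% non-compliance dilutes the delayed-arm mean, it becomes 55 + 0.8 × 15 = 67.
- Natural log: the total is about 50, far from 242.
- Log10: δ = log10(67/55) = 0.0857. With SD 0.21, n = 127 per arm, 254 in all, and power at 242 is 88.8%. An SD of about 0.205 before rounding gives 242 exactly.

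So 242 is roughly reproduced on the log10 scale, with no covariate credit. The log base is not stated and should be.

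**2. Inputs for the illustration.**
- Low flow at <27 weeks 60%, overall 30% (sub-study section 2). Both are given as lower bounds; treating them as exact is an assumption.
- Share <27 weeks w = 534/1600, about one third. The 534 comes from section 8.1 of a superseded protocol version ("About 534 babies are expected to be less than 27 weeks gestation"). V4.0 gives no share, so this is also an assumption.
- Log flow normal within each stratum, with equal SDs (assumption).

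**3. Variance explained by stratum.**
- Low flow at >=27 weeks: (0.30 − 0.60/3) / (2/3) = 0.15.
- Gap between strata: d = z(0.60) − z(0.15) = 0.253 + 1.036 = 1.29 within-stratum SDs.
- Between-stratum variance: (1/3)(2/3)(1.29²) = 0.37. R² = 0.37/1.37 = 0.27.
- Width ratio, unadjusted to adjusted: √1.37 = **1.17**.

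**4. Range.**

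| Share <27 wk | Low flow <27 wk | Low flow overall | Width ratio |
|---|---|---|---|
| 1/3 | 60% | 40% | 1.07 |
| 1/3 | 60% | 30% | 1.17 |
| 1/3 | 70% | 30% | 1.31 |
| 20% | 60% | 40% | 1.03 |
| 40% | 70% | 30% | 1.53 |

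The direction is the same throughout; the size is not well determined.

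**5. Type I error at d = 1.29.**
- Full gestation balance within the sub-study: 2 × (1 − Φ(1.96 × 1.17)) = 2.2%.
- Partial balance: I simulated a 1,600-infant, 25-site trial minimised on site and gestation. An 80% probability of the balancing arm is my assumption. The sub-study was the last 242 infants from a subset of sites. The t-test rejected in about 4.2% of trials with 6 sites (15,000 trials, standard error about 4% too large). It rejected in about 3.6% with 12 sites (30,000 trials, standard error 6% to 7% too large). The gestation-adjusted test stayed at 4.8% to 5.4%.
- No balance: 5%.

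**6. Power, taking the stated 90% at its word.**
- Adjusted: Φ(3.24 × 1.17 − 1.96) = 96.7%.
- Unadjusted, no balance: 90%, a gain of about 7 points.
- Unadjusted, full balance: Φ(1.28 × 1.17) = 93.3% (93.0% in 20,000 simulated trials), a gain of 3.4 to 3.7 points.
- Starting instead from the reproduced 88.8%, adjustment gives about 96%.

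**The case against.** The strongest objection concerns certainty and size. The documents give no R², no SD by stratum and no current share of infants <27 weeks, so 17% is not a figure from the plan. That is correct, and it is used here only as an illustration with its range.

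Second, minimisation runs over the whole trial, while the sub-study covers selected sites for about 12 months and can pause while main randomisation continues (sub-study 4.1 and 4.3). Gestation may therefore be only partly balanced among the 242. This also stands. A reader might infer that the t-test's standard error is simply wrong by 17% and its size 2.2%. That needs full balance inside the sub-study, which the documents do not secure; they do not even say how many sites take part. The 17% compares unadjusted with adjusted intervals. It measures the error in the t-test's own standard error only in the full-balance case.

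Third, a reader might infer that the sub-study is underpowered or its false-positive rate raised. Neither follows. The sample size uses the SD without covariate reduction, the sub-study synopsis foresees enrolment beyond 242, and the error is conservative.

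Fourth, regression is already contemplated. It is, but only optionally, as a secondary analysis and without named covariates.

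Finally, a regression that treats infants as independent would ignore multiple births, which V4.0 section 3.3 randomises separately. That is fair, and the fix allows for it.

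**Conclusion.** The point holds as a loss of efficiency. The primary test omits a factor that the allocation balances and that the sub-study calls prognostic, so its interval is wider than necessary. The excess is about 17% on the illustrative inputs, 7% to 31% with the share held at one third, and 3% to 53% with all open inputs varied. The test is conservative by an amount that depends on balance within the sub-study: a true size of about 2% at full balance and about 4-5% when balance is slight. The power forgone is about 4 points under full balance and up to about 7 without it.

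All these sizes rest on normal log flow with equal SDs in the two strata, on low-flow rates stated only as lower bounds, and on an assumed gestation split. There is no bias, no inflation of false positives, and no shortfall against stated power from this choice. The change is worth making because the gain is nearly free.

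**What to change.** In sub-study 6.2, make the primary analysis a linear regression of log lowest SVC flow on treatment, gestational-age stratum (<27, >=27 weeks) and centre, pooling small centres if needed. Use standard errors that allow for multiple births, in line with section 2.6.1 of the follow-up SAP. Report the retransformed ratio with its 95% confidence interval, and keep the unadjusted t-test as a supporting analysis. State the log base behind the SD of 0.21 in sub-study 6.1.

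The cost is two or three sentences. Both covariates are known at randomisation, and multiple births are already handled in the follow-up analysis. No extra infants or echocardiograms are needed, and the effect measure remains a ratio.

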7 ADMINISTRATIVE ASPECTS

7.1 Trial Management Sub-Committee

An echocardiography Sub-Committee has been appointed to oversee the conduct of the Echocardiography Sub-study. The Chair of the Sub-Committee (A/[name]) will report on the progress and conduct of the study to the main Trial Management Committee (TMC).

The Sub-Committee's responsibilities include protocol development, study planning, monitoring of progress and patient safety. The Sub-Committee will meet as required.

7.2 Independent Data and Safety Monitoring Committee

An Independent Data and Safety Monitoring Committee (IDSMC) will monitor the progress of all aspects of the main APTS study. Echocardiograph assessments will not be submitted for routine assessment by the IDSMC.

Page 46 of 81

7.3 Ethics and regulatory compliance

As for main study

7.4 Confidentiality

As for main study

7.5 Protocol amendments

As for main study

7.6 As for main study Data Handling and Record Keeping

As for main study

7.7 Study Monitoring

As for main study

7.8 Audit and Inspection

As for main study

7.9 Clinical Study Report

As for main study

7.10 Publication Policy

The APTS echo sub-study Committee will draft manuscripts based on the echo substudy data. Authors will have participated in the echo substudy. Manuscript(s) will be submitted to peer-reviewed journal(s).

8 LIST OF SUB-STUDY APPENDICES

Appendix 1. Measurements:

Output (ml/kg/min) = heart rate x (π x diameter² / 4) x velocity time integral / weight (kg)

Superior vena cava flow measurement. A parasternal long axis view using M-mode or continuous 2-D recording of the superior vena cava entering the right atrium for measurement of average superior vena cava diameter (average of minimum and maximum diameters for 5 cardiac cycles). A transverse subcostal view of the superior vena cava entering the right atrium for measurement of superior vena cava flow velocities for calculation of the velocity time integral using pulsed Doppler (for 5 cardiac cycles).

Right ventricular output measurement: The right ventricular outflow tract diameter and Doppler flows are measured from a parasternal long axis view. The diameter is measured in 2-D at the level of the pulmonary valve leaflets in peak systole. Systolic flow velocities are measured by placing the pulse Doppler gate just below the level of the pulmonary valve and the velocity time integral measured in 5 consecutive cardiac cycles. Diastolic flow representing DA shunt flow or pulmonary reflection waves are not measured.

Measurement of ductal diameter and shunt direction: The colour Doppler minimum DA diameter is measured using a high parasternal view. Efforts should be made to ensure that colour Doppler is optimised to avoid 'spill' of colour in surrounding tissues resulting in overestimation of DA diameter. The ductus is measured at point of maximal constriction when there is optimal colour fill. At least 3 cardiac cycles are averaged. The pulsed Doppler DA shunt flow velocity is taken at the pulmonary end to the ductus when a left to right shunt is present and within the DA when bidirectional or right to left shunts are present. The percent time right to left shunt can be calculated by measuring the time interval the shunt is left to right divided by the cardiac cycle.

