7.6 As for main study Data Handling and Record Keeping	
7.7 Study Monitoring	
7.8 Audit and Inspection	
7.9 Clinical Study Report	
7.10 Publication Policy	
8 LIST OF APPENDICES	
Appendix 1: Measurements.	
9 REFERENCES	

1 SYNOPSIS

Aim:

The primary question is: does placental transfusion decrease or increase the risk of low systemic flow, determined by echocardiography in the first 24 hours after birth?

Clinical hypotheses:

Placental transfusion is associated with higher systemic blood flow in the first 24 hours.

Study design:

Sub-study of multi-centre, open label, randomised controlled trial

Study population:

Preterm babies less than 30 weeks gestational age enrolled in the APTS study.

Study assessments

Echocardiography and cardiorespiratory measurements performed at 3, 9 and 24 hours after birth.

Blood collection for Hb/HCT at birth (cord blood) and 6 hours.

Primary Outcome

Lowest SVC flow in 1st 24 hours – this is the lowest SVC recorded from echo assessments at 3 hours (range 3-5), 9 hours (range 6-12 hours) and 24 hours (20 – 28 hours).

Summary statistical methods

242 babies yield 90 % power, assuming 2-sided significance (5%) and 20% noncompliance, to detect a relative difference of 27% - from 55 ml/kg/min in the early cord clamping infants to 70 ml/kg/min in the delayed cord clamping infants ². Additional power will be obtained by further enrolments according to echo substudy resources at individual centers until completion of the main APTS study.

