3 SUB-STUDY OBJECTIVES

In a sub-study of at least 242 babies, the primary question is 'Does placental transfusion decrease or increase the risk of low systemic flow, determined by echocardiography on the first day, in babies < 30 weeks gestation.

HYPOTHESES

Placental transfusion is associated with a reduction in SVC flow ^{1, 2} on echocardiography between 3 and 24 hours after birth.

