4.4 Endpoints

Primary outcome:

Lowest systemic blood flow (defined as lowest recorded SVC flow of 3 measurements at 3, 9 and 24 hours after birth).

Secondary outcomes:

- 1. SVC flow recorded from echo assessments at 3 hours (range 3-5), 9 hours (range 6-12 hours) and 24 hours (range 20-28 hours) in babies less than 30 weeks gestation.
- 2. RVO recorded from echo assessments at 3 hours (range 3-5), 9 hours (range 6-12 hours) and 24 hours (range 20-28 hours) in babies less than 30 weeks gestation.
- 3. Ductal size and shunt direction in first 24 hours
- 4. Absolute change in haemoglobin / haematocrit concentration between baseline (from placenta at birth or, if unavailable, admission Hb/Hct) and at 6 hours after birth from baby
- Hypotension: incidence of persistent hypotension (>15 minutes) receiving treatment with volume expansion or inotropes or corticosteroids. Hypotension is defined as mean BP below the gestation in weeks (mmHg) [approximately <10th percentile for gestation and postnatal age].
- 6. Treatment with volume expansion in 1st 24 hours
 - Type and volume of volume expansion
- 7. Treatment with inotropes in 1st 24 hours
 - Type and dose of inotrope
- 8. Nitric oxide dose
- 9. Indomethacin
 - Timing of administration
- 10. Symptomatic patent ductus arteriosus
- 11. Late intraventricular haemorrhage defined as intraventricular haemorrhage on <14 day HUS not present on initial (3 hour) HUS

Page 43 of 81

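### The echo sub-study's formula for percent right-to-left ductal shunt uses the left-to-right interval, so following it literally records the wrong quantity

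*Supplement*

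**What the plan says.** All references are to the echocardiography sub-study protocol appended to the latest main protocol (version 4.0 by its summary of changes).

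**Shunt measure.**
- Section 4.4, secondary outcome 3: "Ductal size and shunt direction in first 24 hours".
- Section 5.2.3, the parameter recorded at each echo: "Ductal shunt direction %right to left".
- Appendix 1 (Measurements), the only place where the calculation is defined: "percent time right to left shunt can be calculated by measuring the time interval the shunt is left to right divided by the cardiac cycle".

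**Direction of the SVC flow hypothesis.**
- Section 1 (Synopsis): "Placental transfusion is associated with higher systemic blood flow in the first 24 hours".
- Section 3, under Hypotheses: "Placental transfusion is associated with a reduction in SVC flow".
- Section 3, the primary question, which takes no direction: "Does placental transfusion decrease or increase the risk of low systemic flow, determined by echocardiography on the first day".
- Section 6.1, the sample size: "to detect a relative increase of 27%, from a predicted 55 ml/kg/min in the early cord clamping infants to 70 ml/kg/min".

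The summary of changes corrects neither statement and records no formal amendment after version 4.0.

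**The concern.** Appendix 1 names one quantity and gives the recipe for its opposite. An assessor who follows the recipe reports percent left-to-right under the label percent right-to-left. If everyone did so, an arm comparison among ducts with continuous flow would come out with the wrong sign. A two-sided p-value would give no warning, because subtracting every value from 100 leaves the spread and the size of the difference unchanged. If some assessors followed the recipe and others the label, the two codings would be mixed and the difference would shrink.

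Section 5.2.9 has measurements made at each centre by the study fellow, so a single shared reading of the definition cannot be taken for granted.

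The hypothesis wording is a second and lesser inconsistency in the same document. It concerns the sub-study's primary outcome, where the expected direction should be stated only one way.

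**Working it through.** **1. Shunt formula**

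Let L, R and Z be the times in one cardiac cycle C during which ductal flow is left-to-right, right-to-left and absent, so that L + R + Z = C.

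- Quantity named (section 5.2.3): true = 100 x R/C.
- Quantity computed (Appendix 1): written = 100 x L/C = 100 - true - 100 x Z/C.
- Error: written - true = 100 x (L - R)/C.

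*Flow throughout the cycle (Z = 0).* Here written = 100 - true:

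| Left-to-right share of cycle | Written formula reports | True percent right-to-left |
|---|---|---|
| 100% | 100% | 0% |
| 90% | 90% | 10% |
| 80% | 80% | 20% |
| 70% | 70% | 30% |
| 50% | 50% | 50% |
| 30% | 30% | 70% |

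The two agree only at 50%. For arm means, suppose the true values are 30% and 20%, a difference of +10 points. The recorded values are 70% and 80%, a difference of -10 points.

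*Some no-flow time (Z > 0).* The complement rule fails. Assume for illustration L = 50%, R = 30% and Z = 20% of the cycle. The written formula gives 50 against a true value of 30, an error of 20 points. With continuous flow, a true 30 is recorded as 70, an error of 40. Recoding the written 50 as 100 - 50 = 50 does not recover 30.

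*Closed duct (L = R = 0).* Written and true are both 0. Recoding as 100 - x would turn this correct 0 into 100.

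*Purely right-to-left duct (R = C).* Written is 0 and true is 100. A recorded 0 therefore cannot separate a closed duct from a purely right-to-left one. This is why stored values cannot be repaired by arithmetic alone.

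*Mixed coding (Z = 0).* If a fraction p of values is inverted, equally in both arms, the expected difference is (1 - p) x d + p x (-d) = (1 - 2p) x d. The documents give no value for p.

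**2. Direction of the SVC hypothesis**

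The stated effect is a rise: 70/55 - 1 = 0.273, which matches the plan's 27%.

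The sample size statement (242 babies, 90% power, two-sided 5%, 20% non-compliance, log-scale SD 0.21) can be approximated by assuming base-10 logs and equal arms of 121:

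- Delayed-arm mean after 20% non-compliance: 55 + 0.8 x 15 = 67.
- Difference: log10(67/55) = 0.0857.
- Power at SD 0.21: 88.8%, with 254 babies needed for 90%.
- At SD 0.205, which rounds to 0.21, the requirement is 242.

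The plan does not state the log base, so base 10 is an assumption. With natural logs and the 20% dilution applied on the log scale, about 50 babies would be enough.

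On reversing the sign: diluting on the log scale gives 0.8 x log10(70/55) = 0.8 x 0.1047 = 0.0838, and power at 121 per arm is 87.4%. With -0.0838 it is again 87.4%. The two-sided design does not depend on which way the hypothesis is worded.

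The sub-study background also points upward. It reports median SVC flow of 91 ml/kg/min with delayed clamping against 52 with immediate clamping. That observational study is one of the two references attached to the section 3 hypothesis of a reduction.

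**The case against.** **The label is clear and the formula is permissive.** Section 5.2.3 says plainly what to record, and Appendix 1 only says how it can be calculated. A trained echocardiographer may have measured the right interval regardless. This stands as a limit on the consequence: a reader might infer that the shunt data were in fact inverted, and the documents do not show that. It does not excuse the definition, which gives the wrong quantity when followed.

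**The complement rule is not general.** A reader might infer that every recorded value is 100 minus the truth and that the arm difference must change sign. That holds only when flow fills the cycle. Where ducts are closed or have no-flow intervals, the effect depends on how common these are in each arm. This objection stands in full.

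**There are safeguards.** Section 5.2.8 has all echocardiographs collected centrally, the first 10 babies per centre checked by a blinded independent reviewer, and site measurement conditional on an intra-class correlation of absolute agreement above 0.70. If that check covers shunt percentage (the section does not list variables), it could expose a site coding differently from the reviewer. It would not expose an error shared by site and reviewer.

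**The reach is narrow.** Shunt percentage is one recorded parameter behind one secondary outcome of a sub-study, with no analysis specific to it. This also stands.

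**The hypothesis conflict is harmless.** A reader might infer that, with two opposite hypotheses, either result could be called confirmation. That does not follow: the primary question asks about a decrease or an increase, and significance is two-sided. The section 3 line comes straight after a question about the risk of low flow, so a missing word (*low*) is a plausible explanation, though the document does not say so.

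**Conclusion.** The Appendix 1 formula is wrong as written. It yields percent left-to-right under the name percent right-to-left, and nothing elsewhere corrects it.

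The size of the error is conditional. If the formula was followed and ductal flow filled the cycle, the recorded value is 100 minus the true one, and an arm difference in such ducts keeps its size and reverses its sign. With no-flow time the error is 100 x (L - R)/C, and for a closed duct it is zero. Whether any recorded values are affected depends on what sites did, which the documents do not show.

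Ductal diameter and the sub-study's SVC flow primary outcome do not use the formula.

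The hypothesis wording in section 3 does contradict the synopsis, the background and section 6.1, but it is an editorial matter: correcting it changes neither the sample size nor the test.

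**What to change.** 1. In Appendix 1, define percent time right-to-left as the right-to-left interval divided by the cardiac cycle, times 100. State how a closed duct and no-flow intervals are scored.
2. Ask each sub-study centre, and the independent reviewer, which interval was used as the numerator.
3. Where the written formula was used, re-read the shunt timing from the stored recordings, blind to allocation. Do not recode as 100 - x, because that fails for closed ducts and for ducts with no-flow time.
4. In section 3, reconcile the hypothesis with the synopsis and section 6.1. Either *an increase in SVC flow* or *a reduction in low SVC flow* would do so, and the authors should say which was meant.

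The cost is two wording changes and one query to centres. Re-reading is needed only where the query shows that the written formula was applied, and section 5.2.3 already provides for recordings to be stored with a central copy.
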